Individuals responding to recruitment materials or otherwise referred to the study will be pre-screened on

the phone or in person to ascertain preliminary eligibility status. They may have completed the YC Intake Protocol (PRO# 94743) prior to the formal study screening. A series of questions will determine preliminary eligibility, and formal screening appointments will be scheduled for those who meet these eligibility criteria. The comprehensive assessment will include a medical history and physical examination, urine drug testing, semi-structured psychiatric diagnostic interview, and detailed assessment of alcohol and other substance use history. No information obtained during the prescreening will be used as research data. All study related procedures will take place on the MUSC campus within the designated office areas of the Addiction Sciences Division and the Center for Biomedical Imaging.

Inclusion criteria: Participants (*N*=105; 50% female) will be between the ages of 15-19 and may or may not use alcohol. The age of interest corresponds to a time when many adolescents initiate and escalate heavy binge drinking (Johnston et al. 2015), and is therefore the optimal time to

intervene. All participants in the alcohol-using group must meet criteria for heavy drinking, based on quantity and frequency of drinking ([name] et al. 2011; [name] et al. 2012) (see Figure 2). Binge drinking criteria will be used to classify heavy drinking youth, as opposed to alcohol dependence diagnosis, as diagnostic criteria may not be optimal in capturing problematic drinking in youth (Winters et al. 2011). This criteria will be used for the recruitment for all alcohol using participants. Inclusion criteria for non-alcohol-using group: has used alcohol <10 times in their life and has never had a binge drinking episode (4+ females, 5+ males), <5 lifetime experiences with marijuana and none in the past three months; <5 lifetime cigarette use; and no history of other intoxicant use.

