Exclusionary criteria: To maximize our ability to detect effects of interest and minimize potential confounds, we will use rigorous screening criteria. Exclusion criteria for the alcohol-using group will include: not having a parent to consent (for those under age 18); history of alcohol treatment or treatment-seeking; current DSM-5 diagnosis of moderate or severe substance use disorder other than alcohol or cannabis (American Psychiatric Association 2013); positive urine toxicology screen for narcotics, amphetamines, sedatives, hypnotics, or opiates (not prescribed by a doctor); alcohol withdrawal (> 10 on the Clinical Institute Withdrawal Assessment for Alcohol (Sullivan et al. 1989); medical conditions or medications that contraindicate taking NAC; current use of N-acetylcysteine or any supplement containing N-acetylcysteine (must agree not to take any such supplement throughout study participation); medical history of severe asthma (uncontrolled with medication); history of a serious medical, psychiatric, or neurological problem that could affect neural response, brain development, or study participation, including diabetes, seizure disorder, and severe head injury with loss of consciousness; history of learning disability, pervasive developmental disorder, or other condition requiring special education; current use of psychoactive medications that affect cerebral blood flow; noncorrectable visual or hearing problems; non-fluent in English; MRI contraindications (e.g., braces, claustrophobia, irremovable metal implants or piercings); (for females) pregnancy or refusal to use reliable methods of birth control; refusal of blood draw, abstinence from alcohol for >14 days before participation, and use of alcohol <12 hours before scanning (confirmed with breathalyzer). While cigarette and marijuana use will not be exclusionary, we will exclude any participants who are daily users of cannabis or tobacco. Exclusionary criteria for the control group will include all of the above exclusionary criteria except for abstinence from alcohol for >14 days before participation.

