We will also analyze the effects of adolescent binge drinking and sex as a biological variable (SABV), as compared to a non-drinking control group (1:1 sex ratio), to assess the alcohol-related effects within (1) glutamate, GABA, and NAA levels in the ACC, (2) BOLD response to alcohol v. non-alcohol cues in the regions of interest (ACC, insula, striatum, amygdala), and (3) microbiome composition. Two-way analysis of variance (ANOVA) will be used to test the main effects of group and SABV, as well as their interaction (group × SABV). Resulting significant interaction terms will be further tested to assess the effect of group within sex (e.g., difference in glutamate levels between drinking and non-drinking females) and the effect of sex within group (e.g., difference in glutamate levels between male and female heavy drinkers). Clinical and demographic characteristics (age, alcohol use characteristics, GM:BM for MRS data) will be tested for univariate associations with study outcomes; when associated, these variables will be included in an analysis of covariance (ANCOVA). Power analyses and predetermined statistical analyses will ensure findings are robust and unbiased. Summary statistics across groups (means and standard deviations) will be used to estimate SABV and alcohol effect sizes, in order to inform power analysis for a subsequent full-scale studies. SAS will be used for data analysis with a significance level of $\alpha = 0.05$, corrected for multiple comparisons.

Biological markers. Changes in blood phosphatidylethanol (PEth), urinary Ethylglucuronide (EtG), and blood inflammatory marker (IL-6, IL-10, IL-1B, HMGB1) levels from pre- to post-treatment will be explored in relation to participants' change in drinking behaviors. This data can be used to inform power analysis for a subsequent full-scale randomized controlled trial.

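### The secondary drinker-versus-control contrast is read as an alcohol effect, but eligibility lets cannabis, tobacco and other drug use differ between the groups and the planned analysis does not address it

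*Combined protocol and SAP*

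**What the plan says.** The comparison is set out in the protocol under Data Management, in the paragraph on adolescent binge drinking and sex as a biological variable (SABV). Its purpose is "to assess the alcohol-related effects within (1) glutamate, GABA, and NAA levels in the ACC", and likewise in cue reactivity and microbiome composition. The model is simple: "Two-way analysis of variance (ANOVA) will be used to test the main effects of group and SABV", with their interaction. An ANCOVA follows only if a screened variable is associated with the outcome: "Clinical and demographic characteristics (age, alcohol use characteristics, GM:BM for MRS data) will be tested for univariate associations with study outcomes". Group means and standard deviations "will be used to estimate SABV and alcohol effect sizes", which are meant to inform the power of later studies. Significance is 0.05 with a multiplicity correction whose method is not named.

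The eligibility section sets different co-use limits for the two groups:

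- **Controls:** "<5 lifetime experiences with marijuana and none in the past three months; <5 lifetime cigarette use; and no history of other intoxicant use".
- **Drinkers:** "While cigarette and marijuana use will not be exclusionary, we will exclude any participants who are daily users of cannabis or tobacco". The disorder exclusion covers "current DSM-5 diagnosis of moderate or severe substance use disorder other than alcohol or cannabis", so a cannabis use disorder is not a bar. For other drugs there is also an exclusion for a "positive urine toxicology screen for narcotics, amphetamines, sedatives, hypnotics, or opiates" result, but none for lifetime use.

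The overview under Study Design / Methods describes the 30 baseline-only controls as matched on age and gender. The SAP contains no drinker-versus-control model. It lists cannabis variables as covariates under Aims 1 and 2, but those models compare NAC with placebo within heavy drinkers.

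**The concern.** A two-group comparison isolates alcohol only if the groups are otherwise alike on whatever moves the outcome, or if the analysis accounts for the differences. Here the control group is selected for near-abstinence from cannabis, cigarettes and other intoxicants, and the drinker group is not. Any effect of those substances on glutamate, GABA, NAA, cue reactivity or the microbiome would enter the group term and be reported as an effect of drinking. The candidate covariate described as alcohol use characteristics does not help: it says nothing about cannabis or nicotine, and it nearly duplicates group membership.

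The stake is the interpretation of a secondary goal and the planning of later studies. An effect size labelled as alcohol, but partly due to co-use, would mislead the power calculation for any study meant to detect alcohol effects alone.

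**Working it through.** **No plan figure to reproduce.** The documents give no sample size, power or effect size for this comparison. The protocol's power statement (32 participants, d = 1.13, 85%) belongs to the crossover.

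**Step 1: what each safeguard covers.**

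| Safeguard | Cannabis | Tobacco | Other drugs |
|---|---|---|---|
| Control eligibility | Fewer than 5 lifetime uses, none in 3 months | Fewer than 5 lifetime cigarette uses | No history |
| Drinker eligibility | Not daily; use disorder allowed | Not daily | No current moderate or severe disorder; no positive screen for listed classes |
| Matching | No | No | No |
| Candidate covariates | No | No | No |

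The limits are much tighter for controls in every column, and nothing later in the plan closes the gap.

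**Step 2: group sizes.** From the rationale for vulnerable populations, drinkers number 45 + 20 = 65 and controls 10 + 30 = 40. The overview names only the 30 matched controls for this goal, so 65 v 30 is also shown.

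**Step 3: size of a spurious difference (assumptions, not document figures).** Set the true alcohol effect to zero and the within-group SD to 1. Assume that a share p of drinkers co-use, that controls do not, and that co-use shifts the outcome by δ SD. The expected group difference is d = p × δ.

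- p = 0.30, δ = 0.5: d = 0.15
- p = 0.50, δ = 0.5: d = 0.25
- p = 0.70, δ = 0.5: d = 0.35

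**Step 4: chance of a significant result, per test.** Two-sided two-sample t test, with noncentrality d × √(n₁n₂/(n₁+n₂)). The root is √(65×40/105) = 4.976 for 65 v 40, and √(65×30/95) = 4.531 for 65 v 30.

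| d | 65 v 40, α = 0.05 | 65 v 30, α = 0.05 | 65 v 40, α = 0.05/3 | 65 v 40, α = 0.05/8 |
|---|---|---|---|---|
| 0.15 | 11.5% | 10.3% | 5.0% | 2.3% |
| 0.25 | 23.4% | 20.2% | 12.2% | 6.5% |
| 0.35 | 40.7% | 34.8% | 24.9% | 15.3% |

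The last two columns assume Bonferroni, over the three metabolites or over eight outcomes (three metabolites, four regions, microbiome). With δ = 0.3 and the same shares, d is 0.09–0.21 and the uncorrected rate at 65 v 40 is 7.3–17.9%. The expected error in the estimate is d in every column, whatever the correction.

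**Step 5: what adjustment would do.** In 3,000 simulated trials per setting (65 v 40, group-by-sex ANOVA, δ of 0.5 or 0.8), adding a correctly specified co-use indicator returned the group test to a 4.5–5.6% rejection rate and the mean estimate to about zero. The standard error of the group effect rose from about 0.20–0.21 to 0.21, 0.24 and 0.30 with 25%, 50% and 75% co-users. The loss grows because controls contribute almost no co-use, so the adjustment is learned within drinkers.

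**The case against.** **The asymmetry is easily overstated.** A reader might infer that co-use is removed from controls and left unrestricted in drinkers. That is not what the criteria say. Controls may have up to four lifetime uses of marijuana or cigarettes, and drinkers have ceilings of their own. The rules permit an imbalance and bound it. They do not fix its size. This stands.

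**The illustration rests on assumptions.** Neither the co-use share nor any co-use effect is in the documents, and nothing gives a direction or size for tobacco. The uncorrected rates are also not those of the planned analysis, which corrects for multiplicity. Both points stand, and they are why the corrected columns and the smaller control group are shown.

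**The plan may already go part of the way.** The overview calls the comparison group non-using and speaks of neural and microbiome differences, which is more neutral wording. The SAP's Aim 1 cleaning steps pull a drinker-or-control variable alongside cannabis, vaping and cigarette days. So the data are being assembled, but no model is specified that would use them here, and the analysis paragraph still speaks of alcohol effects.

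**Co-use is typical of heavy-drinking youth.** That may be a reason to enrol co-users. It is not a reason to attribute the whole difference to alcohol, and no change to eligibility is asked for.

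**This is a secondary goal.** True. It lies outside the numbered aims, and the randomised within-person contrasts do not depend on it.

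**Conclusion.** The point holds in a limited form. Co-use of cannabis, tobacco and other drugs is a confounder of the drinker-versus-control contrast that the eligibility rules allow and the planned ANOVA or ANCOVA does not address. The contrast as planned therefore cannot support a claim about alcohol alone, nor supply an alcohol effect size for later power analyses.

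The size is unknown. Under the assumptions in the working, the spurious difference is 0.15–0.35 SD for a 0.5 SD co-use shift; the false-positive rate depends on the correction and on which controls are used.

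Two stronger readings are tempting, and the documents support neither. One is that co-use effects will in fact be reported as alcohol effects: that needs a real co-use imbalance and a real co-use effect, and neither is documented. The other is that the trial's main results are compromised: NAC and placebo are compared within the same randomised participants, so this confounding does not reach them.

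**What to change.** Amend the binge drinking and SABV paragraph of the protocol's analysis section, and carry it into the SAP:

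1. Report each group estimate with and without prespecified past-90-day cannabis days and nicotine days from the Timeline Follow-back, regardless of the univariate screen. State that the adjustment rests mainly on variation among drinkers.
2. Add a sensitivity analysis limited to drinkers with no Timeline Follow-back cannabis, nicotine or other drug use in the past 90 days and who, where the substance use history allows, also meet the controls' lifetime limits. The 90-day record alone cannot verify lifetime counts. Report an estimate with a 95% interval, not a pass/fail test: a small subset could miss an agreement criterion even if alcohol has a real effect.
3. Describe the unrestricted contrast, and any effect size taken into later power analyses, as *binge drinkers, with co-use, versus non-using controls*, not as an effect of alcohol alone.

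**Cost.** Plan wording and two further estimates per outcome, on data already collected. The price is precision and a more modest headline claim. If 30–70% of the 65 drinkers co-use, about 45 to 20 remain. With SD 1 and 40 controls, the standard error √(1/n₁ + 1/40) rises from 0.20 at n₁ = 65 to 0.22 at n₁ = 65 × 0.7 = 45.5 and 0.28 at n₁ = 65 × 0.3 = 19.5.

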Neuroscience-Informed Treatment Development for Adolescent Alcohol Use NCT03238300 November 30, 2022

Aim 1:

Hypothesis/aim	Primary: 1a. Quantify the effect of NAC versus placebo on glutamate levels in adolescent heavy drinkers. Using MRS, we will determine the effect of NAC versus placebo on modulating anterior cingulate glutamate levels in heavy alcohol-using adolescents. Hypothesis: Heavy drinking youth will show decreasing levels of glutamate from baseline in the anterior cingulate while on NAC compared to placebo.
Sample size for aim	N= 31 – all with 4 sessions (randomization visit 1, MRI visit 2 & 4, washout visit 3)
Independent variable(s)	NAC v. Placebo: both NAC and placebo were administered twice daily (2400 mg of NAC/day, administered as 1200 mg twice/day) over 10 days
Dependent variable(s)	dACC glutamate levels
Handling of missing data	Only participants with complete data will be included (N=31)
	Complete data = screener, visit 1-4
How outliers and excluded observations will be defined	Participants with all 4 sessions (visit 1-4) will be included. MRS data will be examined for quality using: 1. Linewidth (exclusion: >3 SD from mean) 2. Signal-to-noise ratio (SNR) (exclusion: >3 SD from mean)
	No other outliers will be removed.
Software and specific	Software: R
software modules or packages	Packages: Tidyverse, Imer4 OR glmer4 & ImerTest
Analytic procedure(s)	Generalized linear mixed effect models will examine the effect of NAC vs placebo on neurometabolites (Primary: glutamate) within the adolescent heavy drinking group.
	The primary model will contain the main effect of treatment (NAC vs. placebo), as well as day (period: scan 1 vs. scan 2) and order (sequence: NAC/placebo vs. placebo/NAC) to ensure the crossover design and washout period were successful.
	During model development, random intercepts will be included to account for variations in baseline response levels for individual participants (1 id)

	Covariance structure will be determined based on best fit after trying standard options (e.g., unstructured, Toeplitz, autoregressive, etc.) Model fit will be tested using likelihood ratio tests, Akaike Information Criterion values, and interclass correlation. Parameter estimates and associated 95% confidence intervals for treatment effects on DVs.

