Steps to confirm data assumptions are met	Generalized linear effect mixed models -Check normality of data using Shapiro-Wilks test &/or QQ plot -Divide generalized chi-square by its degrees of freedom to check for dispersion -Compare averages of outcomes to predicted values to check appropriateness of link function -Transform data (if needed) -Check for multicollinearity among predictor variables -Check for carry over effect in crossover models
	Generalized linear models -Plot deviance residuals against fitted values to evaluate linearity for GLM -Look for outliers using leverage & Cook's distance &/or a QQ plot for GLM -Transform data if needed but only on predictor variables
A priori covariates and/or means for identifying important covariates	Baseline levels of clinical and demographic characteristics will be tested for univariate associations with study outcomes; when associated, these variables will be included in the adjusted model development strategy.
	Primary:
	• Age
	• Sex
	Alcohol use variables
	Exploratory:
	Cannabis use variables
A priori interactions to be examined and rules for retaining interaction terms	None.
Planned subgroup or sensitivity analyses	N/A
Level of significance and whether/what corrections for multiple testing will be used	P<0.05, no correction for multiple comparisons

(if null hypothesis significance testing is used)	
Required data	RedCap:
cleaning/formatting steps	 Download baseline variables Age Sex Group (drinker v. control) Mental health measures (anxiety, depression) Download drinking variables from TLFB Total drinking days (visit 1-4) Total drinks/drinking day (visit 1-4) Download other substance use variables from TLFB Total cannabis use days (visit 1-4) Total cannabis use/use day (visit 1-4)
	c. Total vaping days (visit 1-4) d. Total cigarette days (visit 1-4) MRS: 4. Combine excel spreadsheets for all visits and metabolites 5. Remove unnecessary variables a. Final variables: i. Metabolite levels (I.U.) ii. Linewidth iii. SNR Combine RedCap + MRS Data: 6. Merge RedCap and MRS data sheets 7. Remove participants without full data (final N=41) 8. Remove observations that don't meet criteria for inclusion

Aim 2:

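### Alcohol use defines the two groups yet is a candidate covariate in the drinker-versus-control ANCOVA; used for inference, that model's group term no longer estimates the drinker-control difference

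*Combined protocol and SAP*

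**What the plan says.** The combined protocol and SAP, under Analysis and approach, plans a comparison of binge drinkers with non-drinking controls "to assess the alcohol-related effects within (1) glutamate, GABA, and NAA levels in the ACC", and likewise on cue-related BOLD response and the microbiome. The named test is an ANOVA: "Two-way analysis of variance (ANOVA) will be used to test the main effects of group and SABV, as well as their interaction". A significant interaction is followed up by group within sex and by sex within group.

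The same paragraph then gives the covariate rule: "Clinical and demographic characteristics (age, alcohol use characteristics, GM:BM for MRS data) will be tested for univariate associations with study outcomes", and "when associated, these variables will be included in an analysis of covariance (ANCOVA". It names no entry threshold, screening sample or specific alcohol variable, and makes no exception for the group effect. Effect sizes come from elsewhere: "Summary statistics across groups (means and standard deviations) will be used to estimate SABV and alcohol effect sizes".

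The inclusion criteria define both groups by alcohol use. For drinkers: "All participants in the alcohol-using group must meet criteria for heavy drinking, based on quantity and frequency of drinking". Controls must have drunk on fewer than ten occasions in their lives and never have binged.

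The later SAP does not settle the matter. It lists "Group (drinker v. control" among the variables to download, but its glutamate model is fitted "within the adolescent heavy drinking group", and it contains no drinker-versus-control model.

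**The concern.** A covariate in a group comparison should be something on which the groups could reasonably be made equal. Alcohol use is not: it is the exposure under study and the basis of group membership. Adjusting for it asks how drinkers and controls would differ if they drank the same amount. Few or no participants inform that question, so the answer comes from extrapolating a line fitted among drinkers down to zero. It is also not the alcohol-related effect that the paragraph sets out to assess. Age and GM:BM do not have this problem.

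The entry rule adds to it. If the screen is run on the pooled sample, a real group difference itself makes alcohol use correlate with the outcome. The covariate then tends to enter when there is a difference to find. At stake are the adjusted test and the adjusted estimate of the group effect.

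**Working it through.** The documents give no power or effect-size figure for this comparison, so there is none to reproduce. The figures below illustrate the mechanism.

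**Inputs from the combined protocol and SAP.** Drinkers 45 + 20 = 65 and controls 10 + 30 = 40 (rationale for vulnerable populations); the ANOVA terms group, sex and group x sex; alpha 0.05.

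**Assumptions not in the documents.** Pooling to 65 v 40; true difference D = 0.6 SD; one alcohol covariate A (drinking days), gamma-distributed in drinkers with mean 20 and CV 0.3, 0.5 or 1.0, and 0 in controls; pooled univariate screen at p<0.05; alpha not corrected for multiplicity; ANCOVA taken as inferential whenever A enters.

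**Precision.** With A = 0 in controls, the variance inflation of the group term is 1 + (share of controls) x (mean/SD)^2. The share is 40/105 = 0.381.
- CV 0.3: 1 + 0.381 x 11.11 = 5.23, so the SE is multiplied by 2.29.
- CV 0.5: 1 + 0.381 x 4 = 2.52, SE x 1.59.
- CV 1.0: 1 + 0.381 x 1 = 1.38, SE x 1.18.

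**What the adjusted group term estimates.** Let the effect in drinkers be c A^k with mean D. The slope on A is estimated within drinkers. For a gamma variable with shape a and scale t, Cov(A^k, A) = k t E[A^k], Var(A) = a t^2 and E[A] = a t. So slope x mean = k D, and the adjusted group term tends to D - kD = (1 - k)D, whatever the CV.
- Linear (k = 1): 0.
- Square-root (k = 0.5): 0.30.
- Quadratic (k = 2): -0.60.
- Constant (k = 0): 0.60.
- Effect falling with amount, D[1 - 0.5(A - m)/m] with m the mean of A: this equals 0.90 - 0.30 A/m, so the adjusted term is 0.90.

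**Under the entry rule.** The covariate enters only in some samples, so the rule mixes adjusted and unadjusted results. Simulation, 2,000 runs per setting, results in CV order 0.3/0.5/1.0:

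| Effect in drinkers | A enters (%) | Estimate under the rule | Power, ANOVA to rule |
|---|---|---|---|
| Linear | 90/96/100 | 0.03/0.02/0.00 | 77-83% to 5-6% |
| Square-root | 85/86/94 | 0.29-0.30 | about 83% to 12/17/24% |
| Quadratic | not tabulated | -0.57/-0.58/-0.54 | significant in the wrong direction in 23/43/54% |
| Falls with amount | not tabulated | 0.73/0.64/0.63 | not tabulated |
| Constant | 76/63/34 | 0.54-0.56 | about 84% to 28/52/75% |

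With no true effect, the type I error under this rule is 2-4%, so it is not raised.

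**Sensitivity.**
- *Group sizes.* The design overview ties this goal to 30 controls. At 65 v 30, the linear estimate is 0.04/0.02/0.00, and constant-effect power goes from 75-77% to 28/51/68%. At 30 v 30, they are 0.10/0.07/0.03, and about 63% to 19/31/51%.
- *Screen among drinkers only (65 v 40).* The loss is smaller: linear 0.30/0.12/0.00, square-root 0.50/0.46/0.35, constant-effect power almost unchanged at 81-84%. Type I error is then 6-7%.

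The group x sex term was not simulated.

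**The case against.** The strongest reply is that the paragraph names the ANOVA as the test of group and takes effect sizes from unadjusted means and standard deviations. On that reading the ANCOVA is a supplement and nothing important rests on it. Much of this stands: the ANOVA and those effect sizes are untouched. But the covariate sentence is a firm instruction, not a sensitivity analysis, and nothing says which model prevails when the two disagree.

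A second reply is that every magnitude input is assumed. That also stands. The documents give no distribution of alcohol use, the heavy-drinking criteria are in a figure that is not shown, and controls may have up to nine lifetime uses rather than exactly none. The numbers show a mechanism, and results range from near-total loss to almost no change.

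A third is that alcohol use is a sensible covariate for part of this analysis. That is right for the planned contrast of male and female heavy drinkers. Alcohol use does not define those groups, and the binge threshold itself differs by sex (4+ for females, 5+ for males).

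A reader might infer that the adjustment always shrinks the group effect towards zero. Neither the documents nor the algebra supports this: the estimate may shrink, change sign, grow, or stay put with less precision. A reader might also infer that the NAC result is compromised. It is not, because alcohol use does not define NAC or placebo.

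**Conclusion.** The point holds as a defect in a stated covariate rule. In any ANCOVA that includes alcohol use, the group term stops estimating the drinker-control difference. The direction of the change depends on the shape of the relation with amount drunk, which the documents do not supply. Under the assumptions above, a true 0.6 SD difference becomes anything from about -0.55 to 0.73. Where the effect is constant, the estimate stays near its true value, but the ANCOVA standard error is 1.2 to 2.3 times larger.

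The harm is confined to inference on group drawn from the ANCOVA. The documents do not support the stronger conclusion that the planned group test is invalid as it stands, since the named test is the unadjusted ANOVA. The comparison is secondary and non-randomised. The matter is minor to moderate, but worth correcting because the rule is explicit and the remedy is cheap.

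**What to change.** In the binge-drinking and sex paragraph of Analysis and approach:
- Remove alcohol use characteristics from the covariate list for any model that estimates the drinker-versus-control effect, meaning the group main effect and group within sex. Age and GM:BM may stay.
- State that inference on group rests on the model without alcohol variables.
- Allow alcohol quantity and frequency within drinkers, both for dose-response analyses and as covariates in the male-versus-female contrast among heavy drinkers.
- Apply the same exclusion to the group x sex model for consistency; its numerical effect was not evaluated.

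The cost is a few sentences of wording and no new data. If the comparison is later added to the SAP, the same text carries over.
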